Hypothesis testing of the primary efficacy endpoint will be carried out sequentially for $H_0: VE \leq 0\%$ and $H_0: VE < 30\%$. Rejection of the first null hypothesis, $H_0: VE \leq 0\%$ demonstrates a statistically significant vaccine effect. Rejection of the second null hypothesis, $H_0: VE < 30\%$ at Type I error rate of 1-sided 0.0124 is required to meet the statistical success criterion pre-specified for the US-FDA. Should success be declared for the primary endpoint through 0 - 90 days of age, the hierarchical sequential analyses of 0 - 120, 0 - 150, and 0 - 180 days of age will be carried out using the Type I error rate of 1-sided 0.025 and the same null hypothesis.

Two types of analyses concerning the primary efficacy endpoint will be performed prior to the final analysis: recurring futility analyses approximately twice per year after the Northern and

Southern hemisphere winter virus season, and an informational analysis with approximately 1/3 of projected subjects enrolled and followed through at least 90 days.

For the futility analyses and the informational analysis, a Bayesian approach will be used and the analyses will be performed by the Independent Biostatistical Group (IBG) as originally designed. An assumption is made that the distribution of the number of events under the vaccine, x_v , and the number of events under placebo, x_p , are binomial:

$$x_v \sim Bin(\pi_v, n_v)$$
$$x_p \sim Bin(\pi_p, n_p)$$

where π_v and n_v , respectively, are the probability of an RSV event and the total number of subjects in the vaccine group and π_p and n_p , respectively, are the probability of an event and the total number of subjects in the placebo group.

Furthermore, we assume prior distributions for π_v and π_p that are flat, non-informative beta distributions:

$$\pi_v \sim Beta(1,1)$$
$$\pi_p \sim Beta(1,1).$$

Futility will be demonstrated under the primary hypothesis based on the posterior probability that the event ratio, $r = \pi_v / \pi_p$, is less than or equal to 0.60.

Given x_v events out of n_v total subjects in the vaccine group and x_p events out of n_p total subjects in the placebo group, the posterior distributions of π_v and π_p are:

$$\pi_v | x_v \sim Beta(1+x_v, 1+(n_v - x_v))$$
$$\pi_p | x_p \sim Beta(1+x_p, 1+(n_p - x_p)).$$

Sampling from the posterior probability distribution for the event ratio is generated by:

1. Sampling 10 million independent values from the posteriors of π_v and π_p

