13. SAMPLE SIZE CONSIDERATIONS

This study is designed to enroll approximately 4,600 total maternal subjects that include a minimum of 3,000 RSV F vaccine recipients over 4 global RSV seasons.

Assuming a medically-significant RSV LRTI incident rate of 4% in the placebo group and a vaccine efficacy of 65%, then the power of the design to claim success is 87%. [Table 3](#) summarizes the power for different placebo attack rates and vaccine efficacies. Power calculations were performed using the normal approximation (NCSS PASS 14). An estimated PP population size of 4,218 total evaluable infant subjects (2,786 in the RSV F vaccine group and 1,432 in the placebo group to account for 1:1 and 2:1 randomization ratios in Year 1 and the subsequent years, respectively) was used for all calculations.

The target sample size of the safety and efficacy database in third-trimester pregnancy that will be required for licensure is at least 3,000 actively-immunized maternal subjects and their infants. Therefore, the final analysis for efficacy will commence only after a total of 3,000 subjects have been enrolled in the active treatment arm. If no events of a given class are observed among the 3,000 subjects receiving the RSV F vaccine, an approximation to the one-sided upper 95% confidence bound on the rate of SAE occurrence would be 0.1%.

Table 3: Power Calculations for the Primary Efficacy Endpoint (Medically-Significant RSV LRTI Through 90 Days)

Placebo Event Rate	True Event Ratio	Efficacy (1-RR)	Power ^[1]
0.02	0.5	50%	17%
	0.4	60%	41%
	0.35	65%	57%
	0.3	70%	72%
	0.2	80%	92%
0.03	0.5	50%	26%
	0.4	60%	59%
	0.35	65%	76%
	0.3	70%	88%
	0.2	80%	99%
0.04	0.5	50%	34%
	0.4	60%	73%
	0.35	65%	87%
	0.3	70%	96%

Table 3: Power Calculations for the Primary Efficacy Endpoint (Medically-Significant RSV LRTI Through 90 Days)

Placebo Event Rate	True Event Ratio	Efficacy (1-RR)	Power ^[1]
0.05	0.2	80%	>99%
	0.5	50%	42%
	0.4	60%	83%
	0.35	65%	94%
	0.3	70%	99%
	0.2	80%	>99%
0.06	0.5	50%	50%
	0.4	60%	90%
	0.35	65%	97%
	0.3	70%	>99%
	0.2	80%	>99%

^[1] Estimated using normal approximation to rule out H0: Vaccine Efficacy < 30% using one-sided Type I error rate of 0.0124.

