16. DATA HANDLING CONVENTIONS

All statistical analyses will be 2-tailed and assessed at the 5% significance level.

All output will be incorporated into Microsoft Word (including rtf format) or Excel files, or Adobe Acrobat PDF files, sorted and labeled according to the International Conference on Harmonization (ICH) recommendations, and formatted to the appropriate page size(s).

Tabulations will be produced for appropriate demographic, baseline, and safety parameters. For categorical variables, summary tabulations of the number and percentage of subjects within each category (with a category for missing data) of the parameter will be presented. For continuous variables, the number of subjects, mean, median, standard deviation (SD), minimum, and maximum values will be presented.

For all analyses, a two-sided p-value of < 0.05 (one-sided p-value < 0.025 where appropriate) will be considered statistically significant except for the primary efficacy endpoint, medically significant RSV LRTI through 90 day that will be evaluated using a one-sided p value of 0.0124

All references to analysis of GMEU/GMC/ GMT will be interpreted as analysis of the log (base 10) of EU or concentration values or of the reciprocal titers (e.g., the reciprocal titer of 1:160 is the number 160). Values recorded as below the lower limit of quantitation (LLOQ) of the assay for PCA and anti-F IgG will be set to half LLOQ for the purposes of GMEU/GMC, and GMFR analyses. For MN assays, titers will be reported in International Unit (IU) with the LLOQs of 13 for RSV/A and 8 for RSV/B. Titers below the LLOQs will also be set to half LLOQ, 6.5 IU for RSV/A and 4 IU for RSV/B.

For all data analyses and summary tabulations, categories for analysis and presentation will consist of the RSV F vaccine treatment groups. All descriptive statistical analyses will be performed using SAS statistical software Version 9.3 or higher in a Windows environment, unless otherwise noted. Medical history and AEs will be coded using the MedDRA Version 16.1.

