16.4. Multiple Comparisons/Multiplicity

Analysis of the primary efficacy endpoint, medically-significant RSV LRTI in infant subjects, will be performed following a hierarchical closed procedure to control for the overall Type I error rate at 1-sided 0.025. A demonstration of vaccine efficacy through the first 90 days at a Type I error rate of 0.0124 (i.e., lower bound of two-sided 97.52% CI above the pre-specified threshold) will be required prior to testing of subsequent time-points, through 120, 150, and 180 days at Type I error rate of 0.025 (i.e., lower bound of two-sided 95% CI above the pre-specified threshold). Two sets of parallel analyses will be performed for the primary efficacy endpoint, one set for the US-FDA and the other for the ex-US global regulatory submissions (e.g., EMA and WHO) using different success criteria for the primary endpoint, H_0 : Vaccine Efficacy $<$ 30% for the US-FDA and H_0 : Vaccine Efficacy \leq 0% for the ex-US global regulatory submissions. The two sets of analyses will be the same for all other statistical approaches (i.e., methods of analysis, Type I error adjustments, and hierarchical testing approach).

Analysis of secondary and exploratory efficacy endpoints and immunogenicity endpoints will be performed without adjustment for multiple comparisons. The final interpretation of the total vaccine efficacy and the duration of protection will be based on the totality of statistical evidence including immunogenicity results and pre-specified exploratory endpoints; and the clinical importance in discussions with the regulatory agencies and scientific communities.

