16.8. Sensitivity Analyses of the Primary Endpoint

Sensitivity analyses for the primary efficacy endpoints will be performed to investigate the impact of missing specimens and visits for suspected medically-significant RSV LRTI. Whenever possible, supplemental data collected outside the study sites (i.e., hospitalization data within suspected RSV illness episodes) will be used for the sensitivity analysis instead of imputation. If there exists a hospital record for any components of the medically-significant RSV-LRTI endpoint definition, it will be used instead of imputations. These episodes will not be treated as missing.

In order to facilitate the assessment of other reasonable sensitivity assessments, a tipping point analysis will be performed by constructing a grid of all possible $(m_v + 1)$ by $(m_p + 1)$ imputed outcomes for missing values by assigning imputed number of “endpoints” from 0 to m_v in the vaccine group and 0 to m_p in the placebo group. For each possible imputed outcome, the overall vaccine efficacy and the corresponding confidence interval will be constructed using the same statistical method used for the primary efficacy endpoint. The imputed data points in the grid will be evaluated against the H_0 : Vaccine Efficacy $\leq 0\%$.

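### SAP 16.8 reads the missing-data tipping-point grid only against VE ≤ 0%, so the stricter US-FDA criterion (VE < 30% rejected at one-sided 0.0124) has no pre-specified tipping point

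*SAP*

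**What the plan says.** SAP 16.8 deals with specimens and visits missing for suspected primary cases. Hospital records replace missing components where they exist. For what is still missing, "a tipping point analysis will be performed by constructing a grid of all possible" assignments, from 0 to m_v cases in the vaccine arm and 0 to m_p in the placebo arm. In each cell "the overall vaccine efficacy and the corresponding confidence interval will be constructed using the same statistical method used for the primary efficacy endpoint". The section then says "The imputed data points in the grid will be evaluated against the" null of VE ≤ 0%, and names no other threshold.

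The success criteria stand elsewhere:

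- SAP 16.4: "Two sets of parallel analyses will be performed for the primary efficacy endpoint, one set for the US-FDA and the other for the ex-US" submissions. The nulls are VE < 30% and VE ≤ 0% respectively. It adds "The two sets of analyses will be the same for all other statistical approaches", and the list in brackets after that covers the analysis methods, the alpha adjustment and the testing hierarchy.
- SAP 10.3: rejecting VE < 30% "at Type I error rate of 1-sided 0.0124 is required to meet the statistical success criterion pre-specified for the US-FDA".
- SAP 13: the footnote to the power table gives its basis as ruling out "Vaccine Efficacy < 30% using one-sided Type I error rate of 0.0124".
- SAP 16: the exception to the general 5% rule is "medically significant RSV LRTI through 90 day that will be evaluated using a one-sided p value of 0.0124".

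Protocol 10.4.3 lists the sensitivity analyses without a threshold and leaves the detail to the SAP.

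**The concern.** VE ≤ 0% is a legitimate reference for the grid. It is the first null in the SAP 10.3 sequence and the ex-US criterion. But the trial has two success criteria on the same endpoint, and the grid is read only for the easier one. The criterion the trial was powered for has none.

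The grid is the plan's only analysis that varies outcomes still missing after hospital-record substitution. The Kaplan-Meier analysis addresses length of follow-up, the ITT-EFF-I analysis changes the population, and the hospital records fill in some gaps. None of them says how many undetected cases the US claim could absorb. As written, the grid shows how many would overturn any effect at all, which is a later boundary.

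Missing outcomes are a known issue here. The rationale for protocol Version 9.0 records infants who did not meet the endpoint at the site visit, were admitted to hospital 2 to 3 days later, and had no completed study assessments there.

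**Working it through.** **Inputs (SAP 13, 10.3, 16.4).** 2,786 vaccine and 1,432 placebo infants; placebo rate 4%; VE 65%; one-sided alpha 0.0124, so z = 2.2445. Method: log-link Poisson with robust variance and treatment as the only term.

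**Step 1, reproduce the plan's power.** With risks 0.014 and 0.04, SE = √[(1 − 0.014)/(2786 × 0.014) + (1 − 0.04)/(1432 × 0.04)] = 0.2050. Then ln(0.70/0.35)/0.2050 − 2.2445 = 3.381 − 2.2445 = 1.136, and Φ(1.136) = 87.2%. The SAP states 87%.

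**Step 2, planning case before imputation.** Placebo cases: 0.04 × 1432 = 57.3, taken as 57. Vaccine cases: 0.014 × 2786 = 39.0, taken as 39.

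- RR = (39/2786)/(57/1432) = 0.3517, so VE = 64.8%.
- SE = √(1/39 − 1/2786 + 1/57 − 1/1432) = 0.2053.
- Lower 97.52% bound = 1 − 0.3517 × exp(2.2445 × 0.2053) = 44.3%. A fitted robust Poisson model gives the same bound.

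**Step 3, add imputed cases.** Assumption: infants with missing outcomes are already in the denominators. The 30% criterion is lost when the bound falls below 30%, and the 0% criterion when it is 0% or less.

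| Cases added (vaccine/placebo) | Lower bound | Reading |
|---|---|---|
| 11/0 | 30.8% | both hold |
| 12/0 | 29.6% | 30% lost |
| 36/0 | 0.4% | 0% holds |
| 37/0 | −0.9% | 0% lost |
| 20/10 | 32.9% | both hold |
| 26/13 | 30.2% | both hold |
| 28/14 | 29.4% | 30% lost |
| 260/130 | 0.01% | 0% holds |
| 262/131 | −0.06% | 0% lost |

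The first four rows are the most adverse edge, where every missing placebo outcome is a non-case. With 5 added placebo cases, 30% is lost at 18 added vaccine cases and 0% at 45. With 10, the figures are 23 and 53. The 2:1 rows give both arms about the same case fraction among missing outcomes, which means no efficacy among them.

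**Step 4, other planning values.** At a 3% placebo rate and VE 65% (43 and 29 cases), the adverse edge loses 30% at 7 added cases (28.9%; 30.6% at 6) and 0% at 25 (−1.5%; 0.2% at 24). The 2:1 line loses them at 14/7 and 142/71. Of the 25 power-table scenarios, 19 meet 30% before imputation. Across those 19, the adverse edge loses 30% at 1 to 51 added cases and 0% at 12 to 91.

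**Step 5, the whole grid.** m_v and m_p are not in the documents, so these sizes are assumptions applied to the planning case.

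| Missing (vaccine/placebo) | Cells | Pass 0% | Pass 30% | Pass 0%, fail 30% |
|---|---|---|---|---|
| 10/5 | 66 | 66 | 66 | 0 |
| 20/10 | 231 | 231 | 191 | 40 (17.3%) |
| 40/20 | 861 | 853 | 490 | 363 (42.2%) |

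**The case against.** **The boundary is already determined.** Every cell will have a VE and a confidence interval, and the US criterion and its level are fixed elsewhere, so the 30% contour could be read off with no further analytic choice. This is true, and it limits the weight of the point. What is not fixed is that the contour will be drawn and reported: the SAP names one null for this grid, and a 30% reading added after unblinding would be unplanned.

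**SAP 16.4 may cover it.** Read broadly, its sameness clause carries the grid over to the US set. Read by its bracketed list, it does not mention sensitivity analyses, so there is no contradiction with 16.8. Either way, no sentence states the 30% reading.

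**The scenarios are harsh.** This stands as a caution. The adverse edge is extreme, and the 2:1 line assumes no efficacy among missing outcomes. Take 40/20 missing in the planning case. If VE among the missing were 30% and every missing placebo outcome were a case (28/20 added), the lower bound would still be 35.4%, so the US claim would not tip. If VE among the missing were 65% with half the missing placebo outcomes positive (7/10 added), the bound would rise to 46.1%.

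**Cell shares are not probabilities.** This also stands. The 17.3% and 42.2% weight implausible corners equally with plausible cells and depend on assumed numbers missing. They show only how far the two readings can differ.

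**Conclusion.** The point holds. SAP 16.8 evaluates the grid against VE ≤ 0% and nothing in either document sets a reading at 30%, although 30% is the US-FDA criterion. The sensitivity analysis is incomplete; the chosen reference is not wrong, and the primary test is unaffected.

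The practical size depends on how many outcomes remain missing, which the documents do not say. Below 12 missing vaccine-arm outcomes, the planning case shows no difference between the readings. At an assumed 40/20 on the 2:1 line, the US claim holds with 65% of missing outcomes positive (26/40) and is lost at 70% (28/40). The case for acting is that a grid such as 20/10 would, as written, be reported as having no tipping point while part of it overturns the US claim. It should be changed because it is cheap, not because the design is at risk.

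**What to change.** In SAP 16.8, replace the single reference with both: evaluate the Day-90 grid against VE < 30% (US-FDA) and VE ≤ 0% (ex-US), and report both tipping boundaries. In the same sentence, cross-refer to the one-sided 0.0124 level (lower bound of the two-sided 97.52% interval) set in SAP 16 and 16.4, because 16.8 does not restate it and SAP 10.3 also reports a 95% interval.

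The cost is one sentence and a second contour on a grid already planned, with no new data or model. The only downside for the sponsor is that the US claim may look less robust.

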16.9. Calculation of Relative Days and Duration of Event

- Duration of an illness episode or an AE will be calculated as: End Date – Onset Date + 1. For example, for an event that starts on 01 January 2016 and ends on 10 January 2016, the duration of the event will be 10 days, calculated as (10 January 2016) – (01 January 2016) + 1.
- Relative days between the specimen collection of an illness episode and the illness onset date will be calculated as: Specimen Collection Date – Onset Date. For example, for an event that starts on 01 January 2016 and ends on 06 January 2016, the relative days between the illness specimen collection and the onset will be 5 days, calculated as (06 January 2016) – (01 January 2016).
- If two illness events are not separated by at least 7 calendar days (e.g., if an end date of an illness event is 01 January 2016, the onset date of the subsequent illness event has to be 08 January 2016 or later), the two events will be analyzed as one event per the protocol specified window.

17. CHANGES TO ANALYSES SPECIFIED IN THE PROTOCOL

Refer to the RSV-M-301 Protocol, Version 10.0, Dated 02 October 2018 for a summary of the various changes.

18. CHANGES TO THE SAP

18.1. List of Changes from Version 6.0 to Version 6.1

The following changes were made the SAP; no corresponding updates to Version 10 of Protocol RSV-M-301 were required based on these changes.

- Clarified that a time-to-event analysis for the primary efficacy endpoint will be performed as a sensitivity analysis taking potential differences in the length of subject follow-up into account. Minor wording changes to the Introduction, Study Design, and Major Protocol Deviations Assessment sections to be consistent with the protocol. (Section 10.3)
- Clarified that the analysis of SoP will be an exploratory analysis to identify a potential candidate, and that cumulative distribution functions and receiver operating characteristics curves will be used only as screening tools to identify CoRs that have potential to be validated as SoPs (Section 11.1.5).
- Clarified that the statistical significance for the primary efficacy endpoint, medically significant RSV LRTI through 90 days, will be evaluated against a one-sided p-value of 0.0124. (Section 16)
- Revised how <LLOQs are handled for MN assays. MN titers below the LLOQs will be set to half the LLOQ, i.e., 6.5 IU for RSV/A and 4 IU for RSV/B. The method for calculating SCRs was updated to use the same approach as the anti-F IgG ELISA (Sections 11.3 and 16)
- Clarified that missing delivery dates only applies to maternal subjects since no infant subjects had a missing delivery date. This provision was written for maternal subjects who withdrew early so that we can establish the projected end time for their efficacy analysis. (Section 16.6)

18.2. List of Changes from Version 5.0 to Version 6.0

The following changes were made the SAP; no corresponding updates to Version 10 of Protocol RSV-M-301 were required based on these changes.

- Minor wording changes to the Introduction, Study Design, and Major Protocol Deviations Assessment sections to be consistent with the protocol. (Section 1, 2, and 5.3.3.1)
- Wording changes were made to the ITT analysis population definitions to clarify that the mother does not have to have data for the infant, and vice versa. (Section 5.2)
- Updated to clarify the delivery serology sample window for the PP-IMM-M population (Section 5.3.2)
- Category of major protocol deviation involving receipt of any non-protocol vaccine was updated to reflect the current protocol (Section 5.3.3.1)
- Clarified that the protocol deviation listing does not have to be for maternal/infant pairs, but rather for all subjects. (Section 6)

- Added that APGAR scores will additionally be summarized as medians and interquartile ranges. (Section 7)
- Dictionary used to code medical history and unsolicited AEs has been updated (Section 7, 12.1, and 16)
- Dictionary used to code the concomitant medication has been updated (Section 8.2)
- Updated the analysis approach for the infant antibody decay modeling. Instead of using the target visit day for all samples, the actual age of infant subjects in days at the time of sample collection will be used as the exploratory variable in the regression analysis. Also since values reported as < LLOQ do not provide the exact time when the values crossed the LLOQ, they will be excluded from the half-life estimation. (Section 11.1.4)
- Updated how the seroconversion rates are determined (Section 11.1.3) and titers below the LLOQs are handled for the Microneutralization assays that are to be reported in International Units (Section 16)
- Updated the data cleaning plan for the final Day 180 unblinded analysis of efficacy and immunogenicity consistent with the submission provided to CBER on 16 November 2018 (SN 0187) specifying the data cleaning plan for the Day 180 unblinding. The initial plan for cleaning all efficacy, immunogenicity, and safety data for the Day 180 analysis was based on the original plan to submit the BLA with a Day 180 Clinical Study Report (CSR), with only partial Day 365 safety data available at the time of the original BLA submission (reference is made to BLA content proposal submitted in SN 0155; dated 27 April 2018). Per CBER's feedback on this proposal (reference is made to the CBER email dated 11 July 2018), a final CSR with Day 365 data for all subjects will be included in the BLA. Based on this feedback, the data cleaning plan was modified for the safety data at the time of the Day 180 efficacy unblinding. (Section 14.1)
- Added rules for determination of start and stop dates for whether concomitant medications were taken post-vaccination; for missing/incomplete suspect-illness start/stop dates; and for missing/incomplete admission and/or discharge dates for respiratory hospitalizations. (Section 16.6)
- Clarified how death will be handled in the efficacy analyses (Section 16.7)

18.3. List of Changes from Version 4.0 to Version 5.0

In addition to some minor clarifications and corrections, the following changes were made throughout the document to reflect the following changes in the objectives/endpoints and statistical analyses consistent with the Version 10 of Protocol RSV-M-301.

- Updated the study design to reflect the design change that the next analysis will be the final analysis without interim analyses. (Section 3)
- Removed the description of mITT populations, since they are defined the same as the ITT populations. (Section 5.2)

- Updated study objectives and the endpoints to reflect the change made to the study protocol. (Section 5)
- Updated analysis population definitions to clarify the existence of two distinct safety populations (maternal and infant) and to add the review of blinded protocol deviations in determination of the PP populations. (Section 6.3)
- Updated to reflect that there will be no interim analyses. (Section 10)
- Added a description of adjudication to be performed for hospitalizations taken for respiratory symptoms reported on RSV surveillance. (Section 11.2)
- Statistical approaches for the analyses of all efficacy endpoints were changed from the Bayesian method to a frequentist method. The Type I error rate of one-sided 0.0124 will be used for the final analysis without any interim analyses. (Sections 11.3 and 11.4)
- Updated immunogenicity endpoints to make them consistent with the study protocol and additional detail provided for the planned CoR and CoP analyses. (Section 12).
- Added how the GA at birth will be determined for the preterm birth categories (Very preterm and Moderate to late preterm). (Sections 12.6 and 16.6)
- Clarified to state that solicited AEs will not be summarized again in the unsolicited AE tables. (Section 13.4)
- Power calculations were updated based on one final analysis and the frequentist method. (Section 14)
- It has been indicated that the statistical analyses for immunogenicity will be performed using SAS® version 9.4 in a Windows environment. (Section 15)
- Some subgroup analyses have been pre-specified. (Section 16.3).
- Updated to reflect the current plan for handling the multiplicity. (Section 16.4)
- Provided additional details on imputations of EDDs; and concomitant medications associated with RSV surveillance illnesses (Section 16.6)
- Sensitivity analysis proposal for the primary efficacy endpoint was revised for the primary endpoint to simplify and reflect the switching the statistical method to a frequentist method. (Section 16.8)
- Updated Adaptive Design Report to correct randomization ratio for Seasons 2 - 4 from 1:1 to 2:1 (RSV F Vaccine : Placebo). (Appendix 1)

